3.12 Discontinuation of the study

The study may be stopped if, in the judgment of AstraZeneca, trial patients are placed at undue risk because of clinically significant findings that are assessed as causally related to study drug and are not considered to be consistent with continuation of the study.

Regardless of the reason for termination, all data available for the patient at the time of discontinuation of follow-up must be recorded in the eCRF. All reasons for discontinuation of treatment must be documented.

In terminating the study, the Sponsor will ensure that adequate consideration is given to the protection of the patients' interests.

4. STUDY PLAN AND TIMING OF PROCEDURES

Table 1 Study Plan for the Correction Phase

Study Visit	Visit 1	Visit 2 ⁷	Visit 3 ⁵	Visit 4 ⁵	Visit 5 ⁵	EOS ⁶
Correction Phase Day	Screening	Day 1 ⁷	Day 2 ⁵	Day 3 ⁵	Day 4 ⁵	Day 10 ⁶
Written informed consent	X					
Eligibility criteria		X				
Demographics	X					
Medical History		X				
SF-36 v2 questionnaire		X				
Physical exam including weight		X ⁸				X ⁸
Access IVRS/IWRS	X	X	X ⁹	X ⁹	X ⁹	
Study drug (IP) dispensation		X	X ⁹	X ⁹		
Study drug (IP) administration		X	X ⁹	X ⁹		
ECG		X	X ⁹	X ⁹	X ⁹	X
Vital signs		X		X ⁹	X ⁹	X
Concomitant medications		X	X	X	X	X
Adverse events		X ¹⁰	X	X	X	X
Potassium ¹		X ²	X ^{3,11}	X ¹¹	X ¹²	X ¹²
Serum Chemistry ¹		X			X ⁹	X
Hematology ¹		X			X ⁹	X
Aldosterone and renin ¹		X				
Urinalysis ¹		X			X ⁹	X
Urine HCG		X ⁴				X ⁴
IP Reconciliation						X

- All blood potassium samples are analyzed by i-STAT and by the Central Laboratories on all occasions. Serum clinical chemistry, including S-K, hematology and urinalysis will be measured fasting and before administration of ZS. For diabetic patients all blood potassium samples should be collected prior to insulin administration whenever possible.
- Blood potassium will be measured twice 60 (±15) minutes apart within 1 day of first dose administration on Correction Phase Day 1(Visit 2) and at 4 hours (±15 min) after administration of the first dose of ZS. Potassium will be measured again at 90 minutes (±15 minutes) after taking the second dose for patients with i-STAT potassium ≥6.1 mmol/L or <4.0 mmol/L 4 hours after the first dose. The Central Laboratory serum chemistry, hematology, aldosterone and renin samples will be collected at the same time as the 60 minutes i-STAT screening potassium sample, but will be analysed only in confirmed hyperkalemic subjects.

3. Potassium will be measured predose (0 hour) and 1 hour (± 15 min) after the first dose on Correction Phase Day 2 (Visit 3).
4. U-HCG will be performed exclusively for women of childbearing potential. Samples will be analysed locally, and the data will not need to be collected in the database. Pregnant women are excluded from the study.
5. Visit 3, 4 and 5 (Day 2, 3 and 4 for the Correction Phase) are the same as visit 6 Day 1 in the Maintenance Phase for patients achieving normokalemia in the morning the day of the visit. Patients not achieving normokalemia at Visit 4 will be dosed with ZS 10g TID for an additional 24h and then return to the site for Visit 5.
6. EOS in Correction Phase only for patients NOT entering the Maintenance Phase, and occurs 7 ± 1 day after the last administration of IP.
7. Baseline parameters should be measured/collected no earlier than 1 day prior to administration of the 1st dose of study drug on Day 1 (Visit 2). Visits 1 and 2 may be combined into a single visit on the same day.
8. A complete physical examination should be performed within 1 day of administration of the first dose of study drug on Correction Phase Day 1, and targeted physical examination will be conducted on EOS.
9. If subject does not qualify for the Maintenance Phase on/before Correction Phase Day 4.
10. AEs will be collected after the patient has signed informed consent, so during the Day 1 (Visit 2), investigator need to check if any AE happened since from inform consent.
11. Blood potassium will be measured upon return to the clinic to determine if the subject is eligible to enter the Maintenance Phase or if the subject should receive an additional 24 hours of dosing.
12. Central laboratory potassium sample collected as part of the serum chemistry panel.

Table 2 Study Plan for the Maintenance Phase

Study Visit (Visit)	6	7	8	9	10	11	12	13	14	15	16	17	18	19	20	21	22	23	EOS	
Maintenance Phase Day⁵ (Day)	1	2	5	12	19	26	54	82	110	138	166	194	222	250	278	306	334	362	One week after last IP⁶	
Targeted physical exam including weight	X			X		X	X	X	X	X	X	X	X	X	X	X	X	X	X	X
SF-36 v2 questionnaire																				X
Access IVRS/TWRS ⁷	X			X		X	X	X	X	X	X	X	X	X	X	X	X	X	X	X
Study drug (IP) dispensation	X			X		X	X	X	X	X	X	X	X	X	X	X	X	X	X	X
Study drug (IP) administration	X			X		X	X	X	X	X	X	X	X	X	X	X	X	X	X	X
ECG	X			X		X	X	X			X			X			X			X
Vital signs	X			X		X	X	X	X	X	X	X	X	X	X	X	X	X	X	X
Concomitant medications	X			X		X	X	X	X	X	X	X	X	X	X	X	X	X	X	X
Adverse events	X			X		X	X	X	X	X	X	X	X	X	X	X	X	X	X	X
Potassium ^{1,2}	X ^{2,3,8}	X ^{2,8}	X ^{2,8}	X ^{2,8}	X ^{2,8}	X ^{2,8}	X ^{2,8}	X ^{2,8}	X ^{2,8}	X ^{2,8}	X ^{2,8}	X ^{2,8}	X ^{2,8}	X ^{2,8}	X ^{2,8}	X ^{2,8}	X ^{2,8}	X ^{2,8}	X ^{2,8}	X ^{2,8}
Serum chemistry ¹	X			X		X	X	X			X			X			X			X
Hematology ¹				X		X	X	X	X	X	X	X	X	X	X	X	X	X	X	X

Table 2 Study Plan for the Maintenance Phase

Study Visit (Visit)	6	7	8	9	10	11	12	13	14	15	16	17	18	19	20	21	22	23	EOS
Maintenance Phase Day ⁵ (Day)	1	2	5	12	19	26	54	82	110	138	166	194	222	250	278	306	334	362	One week after last IP ⁶
Aldosterone and renin										X									X
Urinalysis ¹					X			X		X				X			X		X
Urine HCG																			X ⁴
IP Reconciliation	X	X	X	X	X	X	X	X	X	X	X	X	X	X	X	X	X	X	X
Patient questionnaire																			X

- All blood potassium samples are analyzed by i-STAT and by the Central Laboratories on all occasions. Serum clinical chemistry, including S-K, hematology and urinalysis will be measured fasting and before administration of ZS. For diabetic patients all blood potassium samples should be collected prior to insulin administration whenever possible.
- Please see Table 6 for details on how to adjust the dose based on the measured potassium values.
- Maintenance Phase Study Day 1 sample will be the same sample as obtained on the last day of the Correction Phase.
- U-HCG will be performed exclusively for women of childbearing potential. Samples will be analysed locally, and the data will not need to be collected in the database. Pregnancies are instead reported on the dedicated Case Report Form (CRF) page.
- During the 12 months Maintenance Phase, the scheduled visit may take place either up to 2 days early or late by Visit 10 and up to 3 days early or late from Visit 11.
- EOS occurs 7±1 day after the last administration of IP
- Access IVRS/IWRS on visit indicated or if patient permanently discontinues dosing before the end of Maintenance phase.
- Central laboratory potassium sample collected as part of the serum chemistry panel.

4.1 Screening/Enrolment period (Visit 1)

Procedures will be performed according to the Study Plan in [Table 1](#).

At screening, consenting patients are assessed to ensure that they meet eligibility criteria. Patients who do not meet these criteria must not be entered in the study.

Patients can be re-screened once during the clinical trial period. The following rule will be applied for the patient who will be ineligible due to the deviation of inclusion criteria No. 3. If the patient is expected to meet the eligibility criteria based on the patient's disease condition, the patient can be re-enrolled (including one re-screening) only once after 30 days or later from the screening failure. In this case, new enrolment number will be allocated to the patient. A new ICF does not need to be signed before re-screening if the original ICF was signed within 30 days and has not been revised.

After a patient has signed ICF at Visit 1, the site investigator will use the IVRS/IWRS to obtain a unique patient enrolment number after collecting the demographic parameters from the patient (including sex, date of birth, race, ethnic group).

4.2 Treatment period

[Table 1](#) and [Table 2](#) provide an overview of the procedures performed at each visit during the treatment period, and further details are provided below. Changing the order of the procedures at a visit, e.g. for logistical reasons, would not constitute a protocol violation if agreed in advance and in writing between the site and the sponsor study physician.

4.2.1 Correction Phase Day 1 (Visit 2)

Patients will arrive in the morning, fasting (except water, coffee or tea, with or without milk and/or sugar, and essential medications) for a minimum of 8 hours prior to potassium sample collection at the clinic. Between 1 and 7 hours may be needed for the visit, during which the following assessments will be performed:

- Administer the SF-36 v2 questionnaire. (The SF-36 v2 needs to be completed before the visit. If not, the patient should complete the questionnaire prior to any other study procedures.)
- Review and confirm the patient eligibility for the study by assessing inclusion and exclusion criteria listed in [Sections 3.1](#) and [3.2](#).
- Collect blood samples for assessment of potassium 60 minutes apart (± 15 min). Potassium will be analyzed using i-STAT, and samples will be prepared for potential shipment to the Central Laboratory for each time-point.
- If either i-STAT potassium value is < 5.1 mmol/L the patient will be declared a screen failure and discontinue from the study.
- If both i-STAT values are ≥ 5.1 mmol/L the following assessments will be performed:

- Collect blood samples for assessment of hematology and clinical chemistry. (This sample can be collected at the same time as iSTAT sample collection. The patient should be informed that samples can be disposed of in case i-STAT potassium level <5.1 mmol/L and this process should be recorded before the sample collection)
 - Collect urine samples for assessment of urinalysis parameters, including a pregnancy test if the patient is a woman of childbearing potential.
 - Aldosterone and renin collected prior to 10 am (1000) after the subject has been in an upright position for at least 2 hours and before recording the ECG and physical examination.
- Obtain vital signs (pulse rate and blood pressure) (Section 5.2.4).
 - Patient medical and surgical history including co-morbidities will be obtained with the review of selection criteria.
 - Perform 12-lead Electrocardiogram (ECG).
 - Perform a complete physical examination including weight, see Section 5.2.2.
 - Review and record the concomitant medications and AEs/SAEs.

Note: The above procedures should be performed within 1 day of the first administration of study drug and before any IP administration.

Patients who meet all inclusion/exclusion criteria will be entered into the trial and the following procedures will take place:

- The site will access the IVRS/IWRS and the system will assign the patient a Correction Phase IP kit.
- The first doses of study IP will be administered as a suspension in water. The patient will be shown/instructed on how to mix and administer the IP, following which the patient is allowed to break the fast.
- 4 hours (± 15 min) after dose administration a potassium sample (i-STAT and Central Laboratory) will be collected.
- Patients with i-STAT potassium levels < 6.1 and ≥ 4.0 mmol/L at the 4 hour (± 15 minutes) post Dose 1 blood draw will be sent home with instructions on how to take the IP. They will be requested to fill out a dosing schedule card indicating when they took the IP. The patient will return to the clinic the following morning of the Correction Phase Day 2 (Visit 3).
- Patients with i-STAT potassium ≥ 6.1 or < 4.0 mmol/L at the 4 hour post Dose 1 blood draw will stay in the clinic and take the second dose of study drug approximately 4-hours after the first dose. They will then remain in the clinic an extra 90 minutes (± 15 minutes) after taking the second dose when another blood

sample for potassium determination (i-STAT and Central Laboratory) will be collected and an ECG will be recorded.

- If the potassium level is > 6.5 mmol/L as determined by the i-STAT at the 90-minute post Dose 2 blood draw, the patient will be discontinued from the study. Patient will return to the clinic 7 (± 1) days later for an EOS visit.
- If the potassium level is ≤ 6.5 mmol/L as determined by i-STAT, and the ECG does not exhibit any of the ECG withdrawal criteria, the patient will be sent home with the 3rd dose of study drug and the dosing card and return to the clinic in the morning of Correction phase Day 2 (Visit 3).

- See section 7.2 regarding how to handle patients with potassium < 3.5 mmol/L.

4.2.2 Correction Phase Day 2 (Visit 3)

Subjects will arrive at the clinic in the morning after fasting for at least 8 hours prior to potassium sample collection.

- The clinic staff will solicit any adverse events, note any changes in concomitant medications, note if the subject has visited a doctor or emergency room since the last visit, examine the investigational product dosing boxes and sachets and make note of the time the doses were taken and any unused investigational products on the eCRF and source documents.
- Potassium values will be evaluated by i-STAT and the Central Laboratory.
- If the i-STAT potassium value is between 3.0 and 3.4 mmol/L inclusive, the subject should not take a study IP doses that day and return the next day to assess potassium.
 - 1 hour (± 15 min) after first serum potassium measurement a potassium sample (i-STAT and Central Laboratory) will be collected.
- If the i-STAT potassium value is between 3.5 and 5.0 mmol/L, inclusive, the subject will enter the Maintenance Phase and complete the procedures detailed in Section 4.2.5.
- If the i-STAT potassium value is ≥ 5.1 mmol/L, the subject will receive an additional 24 hours of ZS 10 g TID and the following procedures will be performed:
 - The site will access the IVRS/IWRS and provide the 7-digit subject identification number. The system will assign the subject an investigational product kit.
 - An ECG will be performed (Section 5.2.3).
 - The morning dose of ZS will be administered in the clinic as a suspension in water.

- 1 hour (\pm 15 min) after dose administration a potassium sample (i-STAT and Central Laboratory) will be collected.
 - Patients with i-STAT potassium levels ≤ 6.5 and ≥ 3.5 mmol/L at the 1 hour (\pm 15 minutes) post Dose 1 blood draw will be sent home with 2 doses of study drug and instructions on how to take ZS. They will be requested to fill out a dosing schedule card indicating when they took the IP. The patient will return to the clinic the following morning of the Correction Phase Day 3 (Visit 4).
 - If the potassium level is > 6.5 mmol/L as determined by the i-STAT at the 1 hour (\pm 15 minutes) post Dose 1 blood draw, the patient will be discontinued from the study. Patient will return to the clinic 7 (\pm 1) days later for an EOS visit.
- See section 7.2 regarding how to handle patients with potassium < 3.5 mmol/L.

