- The clinic staff will solicit any adverse events, note any changes in concomitant medications, note if the subject has visited a doctor or emergency room since the last visit, examine the investigational product dosing boxes and sachets and make note of the time the doses were taken and any unused investigational products on the eCRF and source documents.
- Potassium values will be evaluated by i-STAT and the Central Laboratory.
- If the i-STAT potassium value is between 3.5 and 5.0 mmol/L, inclusive, the subject will enter the Maintenance Phase and complete the procedures detailed in Section 4.2.5.
- If the i-STAT potassium value is < 3.5 or ≥ 5.1 mmol/L following 72 hours of dosing with ZS 10 g TID, the following procedures will be performed:
 - Collect blood samples for assessment of hematology and clinical chemistry.
 - Collect urine samples for assessment of urinalysis parameters.
 - Obtain vital signs (pulse rate and blood pressure) (Section 5.2.4).
 - An ECG will be performed (Section 5.2.3).
 - The site will access the IVRS/IWRS, provide the 7-digit subject identification number, and document that the subject did not qualify for the Maintenance Phase.
 - Subjects will then DISCONTINUE from the study, and receive standard of care at the discretion and the direction of his/her own physician. However, the subject will need to return to the clinic in the morning, fasting for at least 8

[figure not shown]
Clinical Study Protocol
Drug Substance ZS
Study Code D9482C00001
Version 5.0
Date 13 Sep 2018

hours prior to potassium sample collection, 7 (\pm 1) days later after the last administration of IP for an End of Study visit.

Figure 4 Flow chart based on the S-K level: Correction Phase

S-K: Serum potassium, QD: Once daily, TID: Three times daily
 *: Confirmation by an additional measurement after 10 minutes is required.

S-K: Serum potassium, QD: Once daily, TID: Three times daily
*: Confirmation by an additional measurement after 10 minutes is required.

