If a patient develops i-STAT potassium values between 3.0 mmol/L and 3.4 mmol/L, inclusive (confirmed by taking a second potassium measurement after a 10 ± 2 minute interval) during the Correction Phase the subject will be directed to not take any more study drug for the remainder of the day and return the next day to continue in the study. E.g. Patients with potassium values between 3.0 mmol/L and 3.4 mmol/L on Day 2 will not take the drug the rest of the doses on Day 2, and will return fasting to have their potassium tested again on Day 3 and continue their therapy. If the potassium has normalized, the patients will start Maintenance Phase from the day. If patients with potassium values between 3.0 mmol/L and 3.4 mmol/L on Day 3, the patients will not take the drug the rest of the doses on Day 3, and will return fasting to be assessed for entering into the Maintenance Phase on Day 4.

Patients with i-STAT potassium <3.0 mmol/L (confirmed by taking a second potassium measurement after a 10 ± 2 minute interval) should discontinue from therapy.

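### The Correction Phase rules for i-STAT potassium below 3.5 mmol/L differ between the visit sections, Section 7.2, and the synopsis and Section 1.4

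*Protocol*

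**What the plan says.** The protocol deals with low potassium in the Correction Phase in four places.

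- **Visit sections, Days 2 and 3 (4.2.2, 4.2.3).** "If the i-STAT potassium value is between 3.0 and 3.4 mmol/L inclusive, the subject should not take a study IP doses that day", with return the next day. Day 2 alone adds that, 1 hour "after first serum potassium measurement a potassium sample (i-STAT and Central Laboratory) will be collected". Both sections end with a pointer: "See section 7.2 regarding how to handle patients with potassium < 3.5 mmol/L".
- **Visit section, Day 4 (4.2.4).** "If the i-STAT potassium value is < 3.5 or ≥ 5.1 mmol/L following 72 hours of dosing with ZS 10 g TID", end-of-participation procedures follow and the patient is discontinued. The text of this section mentions no repeat reading and has no pointer to Section 7.2.
- **Section 7.2 and the dosing part of the synopsis.** A 3.0-3.4 value counts when "confirmed by taking a second potassium measurement after a 10 ± 2 minute interval) during the Correction Phase". The patient is then told to "not take any more study drug for the remainder of the day and return the next day to continue in the study". Section 7.2 adds examples: a patient held on Day 3 "will return fasting to be assessed for entering into the Maintenance Phase on Day 4".
- **Design text of the synopsis, repeated in Section 1.4.** Normokalemia is 3.5-5.0 mmol/L. A patient who does not meet it on Day 2 or Day 3 receives another 24 hours of ZS 10 g TID. There is no separate branch for low values.

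A footnote to Figure 4 also calls for confirmation after 10 minutes, but the figure is not visible in the text available.

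**The concern.** These rules decide whether a dose is withheld, on which day Maintenance Day 1 falls, and whether a patient leaves the study. If sites can follow different sections in good faith, patients with the same readings will have different exposure and disposition. That affects the Correction Phase summaries, including the proportions normokalemic at 24, 48 and 72 hours in Section 8.4.1. It also affects who can enter the Maintenance Phase analysis sets in Sections 8.3.1 and 8.3.2. Patients with low values would be managed inconsistently as well, which matters in a study whose purpose is safety.

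**Working it through.** The protocol states no figure to reproduce here. The check is to apply each rule as written to the same pair of i-STAT readings.

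**Step 1. The rules side by side**

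| Source | Trigger | Action |
|---|---|---|
| 4.2.2, 4.2.3 (Days 2, 3) | value 3.0-3.4; repeat not mentioned | no dosing that day, return next day |
| 7.2 and synopsis, dosing part | 3.0-3.4 on two readings 10 ± 2 minutes apart | no further dosing that day, return next day |
| 4.2.4 (Day 4) | value < 3.5 after 72 hours of dosing; repeat not mentioned | discontinue |
| Synopsis, design part, and 1.4 (Days 2, 3) | outside 3.5-5.0 | 24 more hours of 10 g TID |
| Synopsis, design part, and 1.4 (Day 4) | < 3.5 or ≥ 5.1 after 72 hours | withdraw |

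**Step 2. Readings run through the rules**

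| Day | Readings | 4.2.2 to 4.2.4 | 7.2 | Synopsis design text and 1.4 |
|---|---|---|---|---|
| 2 or 3 | 3.4, then 3.3 | hold | hold | 24 more hours TID |
| 2 or 3 | 3.4, then 3.6 | hold | not confirmed; next step not stated | 24 more hours TID |
| 4 | 3.4, then 3.3 | discontinue | hold, return next day | withdraw |
| 4 | 3.4, then 3.6 | discontinue | not confirmed; next step not stated | withdraw |

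Where the repeat is 3.6, the visit sections say that "If the i-STAT potassium value is between 3.5 and 5.0 mmol/L, inclusive, the subject will enter the Maintenance Phase". Section 7.2 does not say whether the repeat may be used for that decision, so Maintenance entry is an inference and not a stated outcome.

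**Step 3. Reach of the Day 4 rule**

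10 g TID is 3 doses per 24 hours, so 72 hours is 3 × 3 = 9 doses, as Section 7.2 states. A patient held for the whole of Day 3 has had at most 3 + 3 + 0 = 6 doses by Day 4. Section 7.2 sends this patient to the Day 4 assessment. The discontinuation branch of 4.2.4 is worded only for patients with 72 hours of dosing. If the patient is still below 3.5, or at 5.1 or above, on Day 4, the literal wording of 4.2.4 does not cover the case.

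**Step 4. Section 7.2 on Day 4**

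Its general sentence covers the whole Correction Phase, so a confirmed 3.0-3.4 patient on Day 4 would return the next day. Table 1 has no Correction Phase visit between Day 4 and the EOS visit. The two sections cannot both be followed on Day 4.

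**The case against.** The strongest defence is that 4.2.2 and 4.2.3 are short forms. They end by sending values below 3.5 to Section 7.2, they prescribe the same action, and nowhere do they say that a single reading is enough. On this view Section 7.2 supplies the confirmation step and silence is not contradiction. This has force and softens the Day 2 and Day 3 discrepancy. It does not remove it. The visit sections give a complete instruction before the pointer, and nothing says that 7.2 overrides it. The Maintenance visit sections (4.2.6 to 4.2.10) write the 10-minute repeat into the visit text, so a site could take its absence here as intended. The pointer does not help on Day 4, because 4.2.4 has none.

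It can also be said that Day 4 is the final entry decision, that 4.2.4, the synopsis and 1.4 agree on it, and that the examples in 7.2 stop at Day 3. That is a fair guess at intent, but the general sentence in 7.2 is not limited to Days 2 and 3.

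Several stronger readings are tempting, and the protocol does not support them:

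- **That one low reading could lead to hold, Maintenance entry or withdrawal on the same day.** No section withdraws a 3.0-3.4 patient on Day 2 or 3. Withdrawal arises on Day 4.
- **That the Day 2 1-hour sample has no purpose.** The visit text attaches no decision to it, but the version history says it was added to match Figure 4, which may carry one.
- **That a stated percentage of patients is misclassified.** With an assumed i-STAT repeat SD of 0.05, 0.10 or 0.15 mmol/L and rounding to 0.1, a true value of 3.4 gives a low first reading followed by an unconfirmed repeat with probability 0.841 × 0.159 = 0.13, 0.691 × 0.309 = 0.21 or 0.629 × 0.371 = 0.23. At a true 3.45 it is 0.5 × 0.5 = 0.25. The SD is not in the protocol, and the figures apply only to patients already at the boundary.
- **That Table 4 shows no repeat was intended.** It counts no 10-minute repeats, but Table 5 counts none either, although 4.2.6 to 4.2.10 require them.

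**Conclusion.** The inconsistency is real and lies in the current text. It has three parts:

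1. Whether a 3.0-3.4 value must be confirmed on Days 2 and 3, and what follows if it is not confirmed.
2. What happens to a low value on Day 4, and how Day 4 applies to patients whose doses were held.
3. Whether a low value leads to a hold, as in 4.2.2, 4.2.3 and 7.2, or to further TID dosing, as the design text of the synopsis and Section 1.4 literally says. The synopsis contains both instructions.

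Only patients near or below 3.5 mmol/L are affected. Entry requires readings of at least 5.1, so reaching 3.4 means a fall of at least 5.1 - 3.4 = 1.7 mmol/L within the Correction Phase. The protocol does not say how many patients that would be, and the number may be small. The primary objective is Maintenance Phase safety, Correction Phase outcomes are secondary, and no formal testing is planned. A reader might infer a material bias in the study results, but nothing in the protocol shows one. The correction is still worth making, because the rule governs dose withholding and withdrawal and costs little to fix.

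**What to change.** Reconcile the synopsis (design and dosing parts), Sections 1.4, 4.2.2, 4.2.3, 4.2.4 and 7.2, and Figure 4 into one rule with identical wording. It should state:

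- for each of Days 2, 3 and 4, whether a low value needs confirmation and at what interval;
- what follows when the repeat falls in another band, including 3.5 or above;
- how the Day 4 decision applies to patients who have not had 72 hours of dosing because doses were held;
- whether the further 24 hours of TID dosing in the synopsis and Section 1.4 is meant to include values below 3.5;
- whether the Day 2 1-hour sample informs any decision, checked against Figure 4.

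Which clinical rule to keep is for the sponsor's clinical team. The cost is protocol wording and a site memo. If confirmation is kept, it adds at most one 10-minute repeat sample in what is likely to be a small number of patients.
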